12.5.3.1.2 Modified Cigarette Evaluation Questionnaire

The MCEQ will be administered daily from Days -2 to 5. The baseline will be the last assessment prior to 06:30 AM on Day 1.

All summaries, profiles and analysis will be presented for the CHTP and CC arm.

The change from baseline will be calculated for the five domain scores. The domain scores, along with the change from baseline will be summarized. The answers to the individual questions, along with the domain scores and changes from baseline will be listed.

The profiles of the raw means from baseline to Day 5 for the five subscale scores will be produced.

The analysis will compare each post baseline timepoint in the subscales. A repeated measures ANCOVA model will be used with terms for baseline MCEQ score, sex, average daily CC consumption over the last 6 weeks as reported during screening, product, time-point, and the interaction between product and time-point.

The SAS code will be the same as described in Section 12.5.3.1.1 “Urge-to-Smoke Questionnaire of Smoking Urges Brief”.

LS means for each product along with the difference (CHTP - CC) with 95% CI will be presented in the tables.

All figures, summaries and analyses will be performed on the FAS.

The data will be presented in the below outputs, the TFL number refers to the TFL number in the accompanying TFL shell document:

TFL number	Title
TABLES	
15.2.4.24	Descriptive Statistics of MCEQ Subscales – FAS
15.2.4.25	Analysis of MCEQ Subscales – FAS
FIGURES	
15.1.2.35	MCEQ Subscales Arithmetic Mean and 95% CI– FAS
15.1.2.36	MCEQ Subscales Arithmetic Least Squares Mean Differences and 95% CI – FAS
LISTINGS	
15.3.6.13	Listing of MCEQ Questionnaire Results and Changes from Baseline

12.5.3.1.3 Minnesota Nicotine Withdrawal Questionnaire

The MNWS will be administered daily from Days -1 to 6 for the assessment of Day -2 to Day 5 as it is a 24-hour recall questionnaire. The baseline will be the last assessment prior to 06:30 AM on Day 1.

All summaries, profiles and analysis will be presented for the CHTP and CC arms.

The change from baseline will be calculated for both scores. The two scores, along with the change from baseline will be summarized. The answers to the individual questions, along with the two scores and changes from baseline will be listed.

The profiles of the raw means from baseline to Day 6 for the total scores will be produced.

The analysis will compare each post baseline timepoint for the two scores. A repeated measures ANCOVA model will be used with terms for baseline score, sex, average daily CC consumption over the last 6 weeks as reported during screening, product, time-point, and the interaction between product and time-point.

The SAS code will be the same as described in Section 12.5.3.1.1 “Urge-to-Smoke Questionnaire of Smoking Urges Brief”.

LS means for each product along with the difference (CHTP - CC) with 95% CI will be presented in the tables.

All figures, summaries and analyses will be performed on the FAS.

The data will be presented in the below outputs, the TFL number refers to the TFL number in the accompanying TFL shell document:

TFL number	Title
TABLES	
15.2.4.22	Descriptive Statistics of MNWS Total Scores – FAS
15.2.4.23	Analysis of MNWS Total Scores – FAS

TFL number	Title
FIGURES	
15.1.2.33	MNWS Total Scores Arithmetic Mean and 95% CI – FAS
15.1.2.34	MNWS Total Scores Arithmetic Least Squares Means and 95% CI – FAS
LISTINGS	
15.3.6.12	Listing of MNWS Questionnaire Results and Changes from Baseline

12.5.3.2 Human Puffing Topography Parameters

The HPT assessments will take place on Day -2, Day 1 and Day 4 in the CHTP and CC arms, if CC are compatible with the HPT SODIM[®] device.

The per puff parameters are shown in Table 8 and the per cigarette parameters are shown in Table 9.

The per-cigarette parameters derived from the HPT assessments will be summarized along with their changes from baseline. The per-puff and per-cigarette parameters will be listed. In addition the geometric mean and 95% CI of the geometric mean of the per-cigarette parameters will be presented graphically.

The per-cigarette parameters will be analyzed on Days 1 and 4 separately using an ANCOVA model on the log-transformed HPT parameter with terms for log-transformed baseline score, sex, average daily CC consumption over the last 6 weeks as reported during screening, product.

The SAS code will be the same as described in Section 12.5.1.1 “COHb in blood and urinary concentrations adjusted for creatinine of MHBMA, 3-HPMA and S-PMA in 24 hour collection”.

LS means for each product along with the reduction (i.e. 100% - ratio of CHTP : CC) and 95% CI will be presented in the tables.

All figures, summaries and analyses will be performed on the FAS.

The data will be presented in the below outputs, the TFL number refers to the TFL number in the accompanying TFL shell document:

TFL number	Title
TABLES	
15.2.4.30	Descriptive Statistics of HPT Parameters per Cigarette – FAS
15.2.4.31	Analysis of HPT per Cigarette – FAS
FIGURES	
15.1.2.37	HPT per Cigarette Parameters Geometric Mean and 95% CI – FAS
LISTINGS	
15.3.7.1	Listing of HPT Assessments

12.5.3.3 Human Puffing Topography Questionnaire

The HPT questionnaire will be administered on Days -2, Day 1 and Day 4.

The individual responses will be listed.

The data will be presented in the below outputs, the TFL number refers to the TFL number in the accompanying TFL shell document:

TFL number	Title
LISTINGS	
15.3.7.2	Listing of HPT Questionnaire Results

12.5.3.4 CYP2A6 Activity

CYP2A6 activity will be measured in plasma on Days -1 and 6. In this study the CYP2A6 activity will be calculated using the metabolic ratio of trans 3' hydroxycotinine and cotinine, as described in Section 7.1.4 "CYP2A6". Descriptive statistics of the values and change on Day 6 from Day -1 and supportive listings will be provided.

The analysis will compare the Day 6 values (both absolute and change from baseline) between the CHTP and CC arms. An ANCOVA model will be used with terms for baseline, sex, average daily CC consumption over the last 6 weeks as reported during screening and product. .

The SAS code will be the same as described in Section 12.5.1.1 "COHb in blood and urinary concentrations adjusted for creatinine of MHBMA, 3-HPMA and S-PMA in 24 hour collection"

LS means for each product along with the difference (CHTP - CC) and 95% CI will be presented in the tables

The data will be presented in the below outputs, the TFL number refers to the TFL number in the accompanying TFL shell document:

TFL number	Title
TABLES	
15.2.4.28	Descriptive Statistics of CYP2A6 Activity (%) – FAS
15.2.4.29	Analysis of CYP2A6 Activity – FAS
LISTINGS	
15.3.6.15	Listing of CYP2A6 Activity and Changes from Baseline

12.5.3.5 Relationship between BoExp and NEQ

The analysis of the relationship between NEQ and the biomarkers for the primary and secondary objectives will be reported in a separate report as stated in Section 9 “**Changes from the Protocol Specified Statistical Analysis**”.

12.5.3.6 Ames Mutagenicity Test

The 24 hour urine collection for the Ames mutagenicity test will be on Day -1 and Day 5.

Descriptive statistics of the values and change on Day 5 from Day -1 of the YG1024+S9 mutagenicity will be provided, along with listings.

The data will be presented in the below outputs, the TFL number refers to the TFL number in the accompanying TFL shell document:

TFL number	Title
TABLES	
15.2.4.19	Descriptive Statistics of Ames Mutagenicity Test (YG1024+S9) (units) – FAS
LISTINGS	
15.3.5.1	Listing of Mutagenicity Results and Changes from Baseline

12.5.4 Safety Evaluation

Safety variables monitored in this study include: AEs; vital signs (systolic and diastolic blood pressure, pulse rate, respiratory rate); spirometry; ECG data; concomitant medication, clinical chemistry, hematology, urine analysis safety panel, BMI, physical examination, respiratory symptoms (cough assessment).

The primary analysis of Safety parameters will be conducted on the Safety Population as described in Section 12.1.3 “**Descriptive Statistics**”.

12.5.4.1 Safety Reporting

An exposure emergent AE is defined as an AE that occurs after first product use or that is present prior to first product use and becomes more severe after first product use. All other AEs will not be summarized but provided in listings only.

All AEs occurring from the time of signing of informed consent will be recorded electronically. AEs will be tabulated and listed. However, during the screening period (prior to first product use), only study related AEs will be summarized. The AE listings will include all AEs captured in the database at any time during the study (including those from subjects who were not in the Safety Population).

AEs reported from subjects that have a first product use, but were not randomized will be summarized in a separate column with “Exposed but not using randomized product” as a column header.

Partial dates will not be imputed, but assumptions will be made as follows to assign to product-emergent or not:

Date information	Assign as
Partial date, e.g. --May2012, or -----2011. If month/year is the same as, or later than the month and/or year of Screening.	Product-emergent
Partial date, e.g. --May2012, or -----2011. If month and/or year is earlier than the month and/or year of Screening.	Not product-emergent

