6.3.5 Safety Follow-up Period

During the Safety Follow-up Period (after discharge at Day 6 until Day 13), all subjects are free to smoke their own CC *ad libitum*.

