8.5 Reporting and Follow-Up of Pregnancies

For pregnancies detected between the time point of signature of the ICF to the enrolment of the subject, the subject will be considered as a screen failure and removed from the study. No pregnancy form will be filled, however the diagnosed pregnancy must be captured in the screen failure CRF.

Any pregnancy that occurred after first exposure to the IP and is potentially associated with exposure to the IP, including pregnancies spontaneously reported to the Investigator or designee after the EOS must be reported by the Investigator and followed-up until the pregnancy outcome is reached.

Potential association with exposure to the IP is defined as the conception date being calculated to have been before the date of the last IP exposure.

Confidentiality Statement

Data and information contained in this document are considered to constitute trade secrets and confidential commercial information, and the legal protections provided to such trade secrets and confidential information are hereby claimed under the provisions of applicable law. No part of this document may be publicly disclosed without the written consent of Philip Morris Products S.A.

The Investigator will complete a pregnancy form (provided as a separate document) for all pregnancies diagnosed (including positive urine pregnancy tests).

The procedure to report a pregnancy and provide any additional/follow-up information to [REDACTED] and the Sponsor must be followed in the same manner and within the same timelines as described for a SAE (section 8.3). In addition, each pregnancy has to be reported as a non serious AE. No invasive procedures, including drawing of blood, must be done in such subjects after the discovery of pregnancy.

[REDACTED] will follow up pregnancies only if they were detected after first product use (*i.e.*, after CHTP 1.0 test at Admission). If pregnancies are to be followed-up, they will be followed-up until an outcome is reached (*e.g.*, normal delivery, spontaneous abortion, or voluntary termination). Any pregnancy complication, adverse pregnancy outcome, or maternal complications will be recorded.

The Principal Investigator or designee is responsible for informing the IRB of any pregnancy that occurs during the study and its outcome, according to local regulations.

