12.5.4 Safety Analysis

In general, all safety data will be listed and tabulated on the safety population by product arm, using the approach described in section [12.1.3](#). Safety variables collected during Exposure Period will also be reported by product exposure.

Adverse event data will serve as the primary assessment of safety. Other safety variables monitored in this study include: respiratory symptoms (cough assessment VAS and Likert scales); vital signs (systolic and diastolic blood pressure, pulse rate, respiratory rate); spirometry; ECG data; clinical chemistry, hematology, concomitant medications, and urine analysis safety panel; physical examination.

The number and percentage of subjects with AEs and SAEs will be tabulated by system organ class and preferred term. Summaries will also be presented for AEs leading to withdrawal, AEs leading to death, AEs by relatedness to product exposure, AEs by severity, and laboratory AEs. Tabulations will be performed for both the number of subjects experiencing an event and the number of events.

The number and percentage of subjects with clinical findings will be tabulated by sequence for laboratory parameters. Shift tables showing change from baseline of clinical findings will be provided for: ECGs, physical examinations, and laboratory parameters (both shifts in normal ranges and toxicity grades). Descriptive statistics will be summarized by visit and change from Baseline for laboratory parameters, ECG, respiratory symptoms, and vital signs.

Confidentiality Statement

Data and information contained in this document are considered to constitute trade secrets and confidential commercial information, and the legal protections provided to such trade secrets and confidential information are hereby claimed under the provisions of applicable law. No part of this document may be publicly disclosed without the written consent of Philip Morris Products S.A.

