10.5 Safety Population

The Safety Population consists of all the subjects who had at least one exposure to CHTP1.0 (product test at Admission Day). Subjects in the Safety Population will be analyzed according to actual exposure.

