12.1.3 Descriptive Statistics

For continuous data, summary statistics will include the number of subjects (n), the number and percent of subjects with missing data, the arithmetic mean, arithmetic SD, median, first and third quartiles, minimum, maximum, and number; for log-normal data the geometric mean and geometric CV will also be presented. For categorical data, frequency counts and percentages will be presented. Data listings will include all subject level data collected unless otherwise specified. Summary statistics and statistical analyses will generally only be performed for subjects included in the relevant analysis population. For the calculation of summary statistics and statistical analysis, unrounded data will be used.

Summaries on the Safety Population will be produced by actual exposure. Subjects who tested the product but were discontinued before randomization will be shown in a separate column /table.

The following product labels will be used throughout the TFLs (**Table 17**):

Table 17: Product Labels		
Product	Format used in TFLs	Order in TFLs
Carbon Heated Tobacco Product	CHTP	1
Conventional cigarettes	CC	2

The following stratification labels (**Table 18**) for the TFLs will be used:

Table 18: Stratification Labels	
Stratification Factor	Definition
Sex	male
	female
Daily CC consumption (per day)	<10 ¹
	10-19
	>19

¹ Note that due to inclusion criteria for the study there should not be any subjects with daily CC consumption < 10, therefore this category will not be presented unless there is sufficient data for analysis/presentation (see Section 12.1.5.1 "Insufficient Data for Analysis/Presentation").

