12.5.4.2 Adverse Events

12.5.4.2.1 All Adverse Events

All AE tables will be presented by product.

A general summary table of AEs will be presented including:

- The number of events and the number and percentage of subjects reporting at least one AE.
- The number of events and the number and percentage of subjects reporting at least one study product –related AE, broken down by product relatedness (related to CHTP / CC) and expectedness.
- The number of events and the number and percentage of subjects reporting at least one AE broken down by severity including each subject only once with his worst severity.
- The number of events and the number and percentage of subjects reporting at least one SAE.
- The number of events and the number and percentage of subjects reporting at least one AE leading to any action taken, broken down by action taken related to the product (product use interrupted, product use reduced, product use withdrawn, none), treatment given (yes, no), study discontinuation, other action taken.

Additional summary tables of AEs will be presented with a breakdown of the number of events, as well as the number and percentage of subjects reporting each AE, categorized by system organ class (SOC) and preferred term (PT) coded according to the Medical Dictionary for Regulatory Activities (MedDRA) dictionary (version 18.0):

- The number of events and the number and percentage of subjects reporting at least one AE.
- The number of events and the number and percentage of subjects with at least one AE related to product exposure and expectedness.
- The number of events and the number and percentage of subjects with at least one AE leading to product discontinuation or reduction.
- The number of events and the number and percentage of subjects with at least one AE leading to study discontinuation.
- The number of events and the number and percentage of subjects with at least one AE related to study procedure.
- The number of events and the number and percentage of subjects with at least one AE by severity (mild, moderate, severe).

If a subject has more than one occurrence of the same AE, the subject will be counted only once within a PT with the worst occurrence based on the presentation (e.g., for presentation by severity = most severe, for presentation by relationship = most related). Missing information on the intensity of AE will be counted as severe.

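### Exposure-emergent AEs in the SAP have no end point and no AE table is split by period, so the 5-day Exposure Period is pooled with the days before and after it; the protocol's Exposure Period safety report is missing and its omission is undeclared

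*SAP*

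**What the plan says.** SAP 12.5.4.1 defines emergence: "An exposure emergent AE is defined as an AE that occurs after first product use or that is present prior to first product use" and then becomes more severe. It names no last-use date, lag or period at which emergence stops. Protocol 8.5 identifies first product use as the point "after CHTP 1.0 test at Admission", which is Day -3, before randomization and in both future arms.

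SAP 12.5.4.2.1 adds: "All AE tables will be presented by product". The AE and SAE tables listed in SAP 12.5.4.2 (15.2.6.1 to 15.2.6.9) carry no period in their titles. One extra column is foreseen in SAP 12.5.4.1: "AEs reported from subjects that have a first product use, but were not randomized will be summarized in a separate column". For the allocation of subjects, SAP 10.5 says "Subjects in the Safety Population will be analyzed according to actual exposure", and SAP 12.1.3 says "Summaries on the Safety Population will be produced by actual exposure". Neither section says what actual exposure means once assigned use has ended.

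The SAP's glossary ends the Exposure Period at 11:00 PM on Day 5. Protocol 6.3.4 permits cigarettes on Day 6 once the specified procedures are done. For the follow-up to Day 13, Protocol 6.3.5 says that "all subjects are free to smoke their own CC". Protocol 8.2.1 collects AEs until end of study, and the SAP glossary expects new spontaneously reported events in follow-up.

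Protocol 12.5.4 planned two things: a general tabulation of safety data by product arm, and a further one: "Safety variables collected during Exposure Period will also be reported by product exposure". The same section makes AE data the main safety assessment. SAP section 9 declares that safety shift tables are dropped. It does not mention the Exposure Period report.

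**The concern.** The AE tables are the study's lead safety output. They also go to the medical safety officer (SAP 13.2) and into the topline results (SAP 13.3). A reader will take the CHTP and CC columns as a comparison of the two products during randomized use. As specified, they also hold events from days when all subjects smoked their own cigarettes after one CHTP test, and from days when both arms were free to smoke.

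Three features make the pooling hard to undo from the tables:

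- A subject is counted once per preferred term at the worst occurrence (SAP 12.5.4.2.1). In the severity table, a severe event on Day 10 would replace a mild event of the same term on Day 3.
- Ascertainment changes at discharge. Protocol 8.2.2.2 has active collection up to that point, and subject reporting with a closing phone check afterwards.
- A CC-arm subject's reaction to the Day -3 CHTP test is also emergent. The SAP does not say which column it enters.

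Events unrelated to the randomized contrast can hide a difference between the products or add noise to it. The direction cannot be known in advance. The period-limited view that the protocol planned would have kept the Exposure Period separate.

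**Working it through.** **1. The plan's own duration, reproduced.** Protocol 4.4 states 17 to 61 days per subject. Study days have no Day 0.

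- Confinement, Day -3 to Day 6: 3 + 6 = 9 days.
- Safety Follow-up: 13 - 6 = 7 days.
- Minimum: 1 screening day + 9 + 7 = 17.
- Maximum: 42 + 9 + 7 + 3 = 61.

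Both figures agree with the protocol, so the day count below uses the plan's own calendar.

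**2. The emergent window as written.** It starts at the Day -3 product test (SAP 12.5.4.1 with Protocol 8.5). With no end given, it runs as long as AEs are collected: to Day 13, or to Day 16 if the 3 extra days are used in full.

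| Segment | Study days, to Day 13 | Share of 16 | Study days, to Day 16 | Share of 19 |
|---|---|---|---|---|
| Product test to Day -1 | 3 | 3/16 = 19% | 3 | 3/19 = 16% |
| Exposure Period, Days 1 to 5 | 5 | 5/16 = 31% | 5 | 5/19 = 26% |
| Day 6 onward | 8 | 8/16 = 50% | 11 | 11/19 = 58% |

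These are shares of calendar days. They are not shares of events, because the documents give no AE rates.

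**3. Where the events go.** Protocol 12.5.4 has two layers and the SAP has one.

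- General tabulation. The protocol has it by product arm with no period limit. The SAP has it by product under an actual-exposure rule, also with no period limit.
- Additional tabulation. The protocol has Exposure Period safety variables by product exposure. No listed SAP AE table is limited to that period.
- Declaration. SAP section 9 announces the loss of the shift tables but not of this report.

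The actual-exposure rule in SAP 10.5 is applied to subjects. Read that way, a CHTP-arm subject stays in the CHTP column for the whole emergent window, including Days 6 to 13. A reading by event would need a record of product use after Day 5. Protocol 6.6.1 describes dispensing logs for the confinement period, and no use log is described for follow-up. The subject-level reading is therefore the natural one, but it is an inference.

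**4. Whether a period split is feasible.** Protocol 8.2.1 records start and stop dates and times for each AE, and the SAP glossary fixes the period boundaries to the minute. The SAP already summarizes vital signs and cough by study day (12.5.4.5.3 and 12.5.4.5.6). No new data are needed.

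**The case against.** The strongest defence is that keeping follow-up events with the arm is a sound convention. The protocol added a 7-day follow-up after product use, and counting its events by arm keeps delayed effects visible. The protocol's own general tabulation does the same. Safety is reported descriptively with no test, AEs are tabulated by relatedness to CHTP or CC, and every AE is listed with its date. The column layout also sits in a TFL template that is not among the documents.

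Much of this stands. The overall by-arm table should stay, and the missing report does not itself put follow-up events under CHTP: it removes a second view. The defence does not cover the rest. Relatedness is an open-label judgement, and listings give no incidence by period. The SAP says that it lists all tables, and none of the AE titles carries a period, whereas the cough tables have a separate title by study day. An output planned in the protocol has gone without a declared reason.

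Three stronger readings are tempting but unsupported:

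- That the SAP abandons reporting by exposure. It keeps it for all Safety Population summaries (10.5, 12.1.3). What is lost is the restriction to the Exposure Period.
- That the SAP assigns follow-up AEs to CHTP in breach of its own rule. No sentence makes that assignment, and a rule applied to subjects is not broken by it. The term is simply undefined after Day 5.
- That more than half of the AEs in the CHTP column arise on cigarettes. The ratio 7/(5 + 7) = 58% counts days from Day 1. It treats every subject as back on cigarettes for all 7 follow-up days and assumes equal daily AE rates. At an assumed follow-up rate of one quarter it becomes 1.75/6.75 = 26%. Cigarettes are permitted in follow-up, not certain, and the documents give no rates to choose between these figures.

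**Conclusion.** The point holds as a gap in the specification of the AE tables and as an undeclared departure from the protocol. Emergence is open-ended, no AE table separates periods, and the Exposure Period safety report in Protocol 12.5.4 is neither planned in the SAP nor listed as a change. Its size, in days, is that 5 of 16 study days in the emergent window (31%; 26% of 19) are randomized exposure. The effect on AE incidence cannot be derived from the documents.

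The count rests on first product use being the Day -3 test and on AEs being counted to end of study. The placing of follow-up AEs in the CHTP column rests on the subject-level reading of actual exposure. The primary biomarker analysis is not affected. The change should be made because the lead safety tables otherwise cannot show AEs during randomized use, but it does not threaten the study's main conclusion.

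**What to change.** In SAP 12.5.4.2, present tables 15.2.6.1 to 15.2.6.3 and 15.2.6.7 also by AE onset period, using boundaries that the SAP already defines:

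1. Product test to Day 1, 06:29 AM.
2. Exposure Period: Day 1, 06:30 AM to Day 5, 11:00 PM.
3. After Day 5, 11:00 PM to end of study.

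State that an AE which is emergent because it worsened is placed by the time of worsening. Apply the worst-occurrence rule within each period. Use the Exposure Period tables to describe AEs by product exposure, as Protocol 12.5.4 planned. Keep the overall by-product tables, with a footnote that both arms may use cigarettes from Day 6.

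The third period should not be cut at the first cigarette on Day 6, because the Day 6 schedule does not plan to record that time. It should be described as time after assigned use, not as time on cigarettes: it includes the night of Day 5 to Day 6, and resumption is optional.

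State in SAP 10.5 and 12.1.3 how actual exposure applies before Day 1 and after Day 5. Reconcile those sections with SAP 12.5.4.1 and Protocol 12.5.4, and record any departure that remains in SAP section 9.

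The cost is a short SAP amendment and reruns of four existing tables on onset dates and times already collected. The downside is a few more descriptive tables with small counts.

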12.3.3 Medical History and Concomitant Diseases

Medical history is defined as any condition that started and ended prior to Screening. Medical history will be coded using MedDRA version 18.0 and listed separately by product, System Organ Class (SOC) and Preferred Term (PT) within SOC.

Medical History will be summarized by product, SOC and PT for the FAS.

Concomitant disease is defined as any condition diagnosed at Screening or was ongoing at Screening. Concomitant disease will be coded using MedDRA version 18.0 and listed separately by product, SOC and PT within SOC.

Concomitant disease will be summarized by product, SOC and PT for the FAS.

Partial dates will not be imputed, but assumptions will be made as follows to assign to either medical history or concomitant diseases:

Date information	Assign as
Missing stop date	Concomitant disease
Partial date, e.g. --May2012, or ----2011. If month/year is the same as, or later than the month and/or year of Screening.	Concomitant disease
Partial date, e.g. --May2012, or ----2011. If month and/or year is earlier than the month and/or year of Screening.	Medical history

The data will be presented in the below outputs, the TFL number refers to the TFL number in the accompanying TFL shell document:

TFL number	Title
TABLES	
15.2.1.6	Summary of Medical History – FAS
15.2.1.7	Summary of Concomitant Diseases – FAS
LISTINGS	
15.3.1.9	Listing of Medical History and Concomitant Diseases

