12.5.4.5 Vital Signs, Physical Findings and Other Observations Related to Safety

12.5.4.5.1 Prior and Concomitant Medication

Prior medication is defined as any medication that started and ended prior to Screening. Concomitant medication is defined as any medication starting on or after Screening. or medications that started prior to Screening and are ongoing at Screening.

All medications will be listed by product using PT and Anatomical Therapeutic and Chemical (ATC) codes (World Health Organization - Drug Dictionary Enhanced [WHO-DDE] March 2015 C format). A flag will be presented on the listing indicating whether the medication is prior or concomitant. Partial dates will not be imputed, but assumptions will be made as follows to assign to either prior or concomitant:

Date information	Assign as
Missing stop date	Concomitant
Partial date, e.g. --May2012, or -----2011. If month/year is the same as, or later than the month and/or year of Screening.	Concomitant
Partial date, e.g. --May2012, or -----2011. If month and/or year is earlier than the month and/or year of Screening.	Prior

Prior and concomitant medications will be listed by product. Concomitant medications will be summarized for the Safety Population showing the number (%) of subjects who used the medication at least once by product and by ATC 1st and 2nd levels and preferred drug name. Listings will display original dates (no imputation).

The data will be presented in the below outputs, the TFL number refers to the TFL number in the accompanying TFL shell document:

TFL number	Title
TABLES	
15.2.6.11.1	Summary of Prior Medication by Anatomical Therapeutic Classes (ATC) 1 and 2 – Safety Population
15.2.6.11.2	Summary of Prior Medication by Preferred Drug Name – Safety Population
15.2.6.12.1	Summary of Concomitant Medication by Anatomical Therapeutic Classes (ATC) 1 and 2 – Safety Population
15.2.6.12.2	Summary of Concomitant Medication by Preferred Drug Name – Safety Population
LISTINGS	
15.3.6.3	Listing of Prior and Concomitant Medication

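### SAP 12.5.4.1 defines emergent AEs by first product use but sorts partly dated AEs by the month or year of Screening

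*SAP*

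**What the plan says.** **Definition.** SAP 12.5.4.1: "An exposure emergent AE is defined as an AE that occurs after first product use". An AE already present that becomes more severe after first use also qualifies. For the remainder: "All other AEs will not be summarized but provided in listings only". The same section adds that "during the screening period (prior to first product use), only study related AEs will be summarized".

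**First product use.** Protocol 7.3.4 places the CHTP 1.0 product test on Day -3, after enrolment. Protocol 8.5 explains first product use as "after CHTP 1.0 test at Admission". SAP 12.5.4.1 itself speaks of subjects who had a first product use but were not randomized, which fits only the Day -3 test.

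**Partial dates.** SAP 12.5.4.1 introduces its date table with: "Partial dates will not be imputed, but assumptions will be made as follows to assign to product-emergent or not". The table assigns an AE as product-emergent on this condition: "If month/year is the same as, or later than the month and/or year of Screening". It is not product-emergent only when the month or year is earlier than that of Screening.

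**The same rows elsewhere.** SAP 12.3.3 and 12.5.4.5.1 use the same two partial-date rows. There the categories are defined by Screening: "Medical history is defined as any condition that started and ended prior to Screening", and "Prior medication is defined as any medication that started and ended prior to Screening".

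**Collection.** Protocol 8.2.1 and 8.2.2 collect AEs from signature of the consent form until end of study, with start and stop dates and times. Protocol 9.1 puts Screening 1 to 42 days before Admission.

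**The concern.** The definition and the date rule use different reference events in one section. Screening is the right reference for medical history and prior medication, but not for emergence. The wording appears to have been carried across without changing the reference event.

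An AE that belongs to the study starts after consent, so its month or year will rarely be earlier than that of Screening. The not-emergent row therefore has almost nothing to catch. An unrelated Screening-period AE goes to the listings only if it is fully dated, but into the emergent tables if it is partly dated. Completeness of the date, not timing, decides. Protocol 12.5.4 makes AE data the primary assessment of safety, so the rule should follow its own definition.

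**Working it through.** The plan gives no figure to reproduce here. The check applies the rule to an example and then to a calendar.

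**Example.** Screening 20 March, product test 20 April, AE dated only as March.
- By definition: March is before first use, so not emergent unless the AE worsened after use.
- By the SAP table: March is the Screening month, so product-emergent.
- By a first-use reference: March is earlier than April, so not emergent.

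**Calendar count.** Inputs: gap *g* from Screening to Day -3, taken at 1, 14, 28 and 42 days within the 1 to 42 of Protocol 9.1; AE onset on any day from Screening on (Protocol 8.2.1). Assumption: each of the 365 days of 2015 is equally likely as the Screening date. Day -3 and later count as post-use.

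Rule as written: 100% of pre-use days and 100% of post-use days are called emergent. This follows directly from starting the count at Screening; it restates the collection rule and is not separate evidence.

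Rule with first use as reference: a pre-use day is reclassified when a month start (or year start) falls after it and no later than Day -3. For one such boundary, the number of reclassified days summed over Screening dates is 1 + 2 + … + *g* = *g*(*g*+1)/2. The total number of pre-use days is 365*g*. Hence:
- month-only, up to 28 days (at most one boundary in the gap): 12 × (*g*+1)/730
- year-only: (*g*+1)/730

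Month-only: 24/730 = 3.3%, 180/730 = 24.7%, 348/730 = 47.7%. At 42 days two month starts can fall in the gap, so the direct count is used. Year-only: 2/730, 15/730, 29/730 and 43/730. The direct count agrees throughout:

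| Gap (days) | Month-only: still emergent | Month-only: reclassified | Year-only: still emergent | Year-only: reclassified |
|---|---|---|---|---|
| 1 | 96.7% | 3.3% | 99.7% | 0.3% |
| 14 | 75.3% | 24.7% | 97.9% | 2.1% |
| 28 | 52.3% | 47.7% | 96.0% | 4.0% |
| 42 | 35.0% | 65.0% | 94.1% | 5.9% |

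All post-use days remain emergent, so the change loses no AE that starts after first use.

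**Limit of the fix.** Screening 5 April, first use 20 April, true onset 10 April recorded only as April: emergent before and after the change.

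**Cough labels.** SAP 7.2.6 asks about the previous 24 hours, and SAP 11.3 sets the assessment before product use on Days -1 to 5, as for MNWS. SAP 7.2.4 shifts MNWS from Days -1 to 6 to Days -2 to 5. SAP 12.5.4.5.6 summarises cough by day with no shift. Cough collected on Days -1, 1, 2, 3, 4, 5 and 6 mainly recalls Days -2, -1, 1, 2, 3, 4 and 5. A Day 1 cough result therefore describes cigarette smoking on Day -1 in both arms.

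**The case against.** The strongest reply is that the rule will seldom be used. Protocol 8.2.1 asks for start and stop dates and times, AEs are actively collected in confinement (Protocol 8.2.2.2), and missing data are queried (Protocol 11.2.1). There may be no partly dated AE at all. That stands, and it keeps the point small.

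It can also be said that the sentence on Screening-period AEs already keeps unrelated pre-use events out of the summaries. The SAP does not say whether that sentence or the table prevails, so the conflict remains.

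It would go too far to say that the not-emergent row can never be reached. Screening may run over more than one day (Protocol 9.1), a worsening pre-existing condition might carry its older onset date, and the table does not say whether it means the start or the stop date. Nearly every partly dated study AE is as far as the documents go.

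A reader might also infer that AEs between the Day -3 test and Day 1 have no planned place for subjects later randomized. The documents do not support making that a finding. Protocol 12.5.4 tabulates safety data by product arm and adds that Exposure Period safety variables are also reported by product exposure. SAP section 3 leaves table detail to a separate template that is not available here.

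On cough, the reply is that this is labelling only. That is right: no value changes.

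**Conclusion.** The date rule is wrong as written: it calls emergent some AEs that the definition in the same section excludes. The point is minor. The rule can only add events to the emergent tables, which is the conservative direction. The added events start before the Day -3 test and so before randomization on Day -1, so a reader should not infer that they favour an arm. The AE tables are descriptive; no primary endpoint, alpha or power is touched.

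The calendar percentages are shares of pre-use days, not of AEs, and rest on uniform Screening dates at the stated gaps. The number of partly dated AEs is unknown. Nor should a reader infer that misclassification needs Screening to fall in an earlier month than first use, or that re-anchoring removes it all: pre-use AEs in the same month as first use are called emergent under either rule.

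The cough table is inconsistent with the MNWS convention, but only in its day label.

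**What to change.** In SAP 12.5.4.1, compare the partial AE onset date with the month or year of first product use (the Day -3 CHTP 1.0 test). Assign not emergent when the available date parts are earlier, leaving the existing provision for AEs that worsen after first use in force. Keep same-month and undeterminable cases as emergent. The rows in SAP 12.3.3 and 12.5.4.5.1 stay as they are. This costs one line of text and needs no new data.

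Optionally, report cough by the recalled day as SAP 7.2.4 does for MNWS, or state the recalled day in the by-day table. At the same time reconcile Protocol 7.8.2, which has cough assessed irrespective of time, with the window in SAP 11.3, and the MNWS profile to Day 6 in SAP 12.5.3.1.3 with the shift in 7.2.4. These are label and wording changes only.
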